## **17.1.1 All Adverse Events**

Adverse events will be summarized by worst severity per subject, using MedDRA version 19.0 preferred term as event category and MedDRA 19.0 primary system organ class (SOC) body term as Body System category.

Adverse events summaries will be ordered in terms of decreasing frequency for SOC, and PT within SOC, as well as alphabetically for SOC, and PT within SOC.

With respect to TEAEs by severity, subjects will be counted only once for multiple events in the same SOC, by worst severity experienced. If a subject experiences more than one TEAE within a PT, he/she will be counted only once in the PT for the greatest severity he/she experienced. If severity is missing for an event, the greatest severity will be assumed.

With respect to TEAEs by severity, subjects will be counted only once for multiple events in the same SOC, by strongest/closest relationship with IP. If the subject experiences more than one TEAE within a PT, he/she will be counted only once in the PT for the strongest relationship to IP he/she experienced. If relationship to study treatment is missing for an event, the strongest relationship will be assumed.

Adverse events related to trial treatment are those events with relationship missing, unknown or yes.

In case a subject had events with missing and non-missing grades, the maximum of the nonmissing grades will be displayed.

*Treatment* refers to the following trial treatments administered, Biltricide®, rac-PZQ ODT, L-PZQ ODT and includes the overall/total group. The following overall frequency tables will be prepared. In addition, the tables will be provided by PT and primary SOC in alphabetical order:

- TEAEs by cohort
- TEAEs by cohort and severity
- TEAEs by cohort and relationship to IMP
- TEAEs by treatment
- TEAEs by treatment and severity
- TEAEs by treatment and relationship to IMP
- TESAEs by treatment
- TESAEs by treatment and severity
- TESAEs by treatment and relationship to IMP

The following listings will be prepared:

- TEAEs
- TESAEs
- TEAEs leading to subject withdrawal
- TEAEs leading to death

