8.5.4 Analysis of Safety and Other Endpoints

Values for all safety variables will be listed by subject and time point. Where appropriate, safety variables will be summarized using descriptive statistics.

Adverse events (AEs) will be coded by the Medical Dictionary for Regulatory Activities (MedDRA) preferred terms, and all summary tables for AEs will be organized by these categories. Frequency counts and percentages will be presented for subjects with at least 1 treatment emergent AE within each system organ class and preferred term, separated by treatment group. Treatment-emergent AEs will also be summarized by relationship to treatment and by severity within each treatment group.

By-patient listings of clinical laboratory data and vital signs will include indications of value that are outside the reference ranges, and values that are clinically significant. Tables describing out-of-reference range shifts will be provided for clinical laboratory test results and vital signs as appropriate and by treatment arm.

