## 17.3 Clinical Laboratory Evaluation

Laboratory values (including corresponding normal ranges) will be used for summary statistics and shift tables.

Quantitative data will be examined for trends using descriptive statistics (mean, SD, median, Q1, Q3, minimum, and maximum) of actual values and changes from baseline to each visit over time. The changes computed will be the differences from baseline (Day 1 samples) to end-of-trial (Day 14 / early withdrawal). Qualitative data based on reference ranges will be described according to the categories (i.e. Low, Normal, High). Only the 'high' and 'low' categories will be flagged. The number of subjects with clinical laboratory values below, within, or above normal ranges at baseline compared to endpoint will be tabulated for each test by treatment. Shift tables of baseline versus endpoint (as well as the worst value at any post-baseline visit) will be presented. In case of missing data LOCF will be applied.

Laboratory values that are outside the normal range will also be flagged in the data listings, along with corresponding normal ranges. Any out-of-range values that are identified by the investigator as being clinically significant will be shown in a data listing.

Baseline (Day 1) is the last measurement prior to the first dose of any trial treatment.

Subjects without post baseline laboratory samples will be excluded from analyses with respect to change from baseline summaries.

Data will also be presented for absolute and change from baseline results using boxplots, by time point/visit.

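### Serious adverse events are tabulated only by product with doses pooled, so this dose-finding trial has no planned table of the SAE rate at each dose

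*SAP*

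**What the plan says.** SAP 17.1.1 lists nine adverse event frequency tables and says that *treatment* in them "refers to the following trial treatments administered, Biltricide®, rac-PZQ ODT, L-PZQ ODT and includes the overall/total group". Under that definition the L-PZQ column holds 30, 45 and 60 mg/kg together, the rac-PZQ ODT column holds 40 and 60 mg/kg, and the Biltricide column holds both commercial regimens.

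The nine tables fall into three sets:

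- TEAEs by cohort: overall, "TEAEs by cohort and severity", and by relationship.
- TEAEs by treatment: the same three.
- TESAEs by treatment: overall, "TESAEs by treatment and severity", and "TESAEs by treatment and relationship to IMP". There is no by-cohort counterpart.

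For laboratory data, SAP 17.3 says that the numbers of subjects below, within and above the normal range "at baseline compared to endpoint will be tabulated for each test by treatment". It does not define the term there. Protocol 8.5.4 is more specific: "Tables describing out-of-reference range shifts will be provided for clinical laboratory test results and vital signs as appropriate and by treatment arm".

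**The concern.** The Part 1 primary objective (protocol 4.1) asks for a dose that is both effective and acceptably safe, and the first secondary objective (4.2) concerns safety at different doses. The comparison of interest is between doses, yet the only SAE rates that the SAP will produce are between products. If serious events cluster at the highest L-PZQ dose, the L-PZQ column averages them with two lower-dose arms. A reader of the study report would have to count cases from a listing and supply the denominators to see the gradient.

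The laboratory wording raises a related but weaker question. Under protocol 7.4.1.1, an abnormal laboratory value is not an adverse event unless it has clinical signs or symptoms, leads to discontinuation, or is judged medically important. A dose-related shift in transaminases may therefore never reach the by-cohort TEAE tables, so the grouping of the laboratory tables should be beyond doubt.

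**Working it through.** **Inputs.** 60 enrolled subjects in each of C1 to C7 (SAP 6.1). C5, C6 and C7 are L-PZQ 30, 45 and 60 mg/kg. C7 opens only if the SMC approves. The documents give no expected SAE rate, so the event counts and risks below are illustrative. Only the denominators come from the plan.

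**The plan's own figures.** 50 evaluable at about 17% dropout gives 50/0.83 = 60.2, which agrees with 60 per arm. 6 × 60 = 360 and 7 × 60 = 420, as stated. After the first 40 per arm, the 1:1:1:1:1:1:3 stage adds 20 to each of C1 to C6 and 3 × 20 = 60 to C7. The arms are therefore equal in size.

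**Formula.** Pooled L-PZQ rate = (n5·p5 + n6·p6 + n7·p7)/(n5 + n6 + n7). With equal arms this is (p5 + p6 + p7)/3.

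**Events in C7 only** (Clopper-Pearson 95% CI):

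| SAEs, all in C7 | By cohort | Pooled L-PZQ |
|---|---|---|
| 3 | 3/60 = 5.0% (1.0% to 13.9%) | 3/180 = 1.7% (0.3% to 4.8%) |
| 6 | 6/60 = 10.0% (3.8% to 20.5%) | 6/180 = 3.3% (1.2% to 7.1%) |

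The ratio is 180/60 = 3.0. With 50 per arm it is 150/50 = 3.0, so dropout spread evenly over the arms does not change it.

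**Other patterns:**

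- Risk of 2% at the two lower doses and 10% in C7: pooled (2 + 2 + 10)/3 = 4.7%, a 10/4.7 = 2.1-fold dilution.
- Risk rising 0%, 2.5%, 5%: pooled 2.5%, a 2.0-fold dilution.
- C7 not opened, events only in C6: 120/60 = 2.0-fold.
- The rac-PZQ ODT and Biltricide columns each pool two arms, so their limit is also 120/60 = 2.0-fold.

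**Laboratory tables.** No arithmetic applies, so the texts are set side by side. One reading carries the product definition over from 17.1.1, because 17.3 uses the same word. Against it:

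- SAP 11 presents results by treatment group unless told otherwise.
- SAP 10.2.1 lists treatment group as seven dose-specific levels.
- Protocol 8.5.4 asks for tables by arm.
- SAP 9 declares no departure from the protocol.
- In 17.3 the phrase is attached to the range counts; the next sentence, on shift tables, has no grouping term at all.

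The weight of the text favours dose-specific tables. The wording is ambiguous, but it does not establish pooling.

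**The case against.** The strongest reply is that little is hidden. Every treatment-emergent SAE is also a TEAE and is counted in the by-cohort tables, including those by severity and relationship. SAEs are listed by subject (SAP 17.1.1 and 17.2.2), and deaths are listed by cohort with dosing information (17.2.1). With a handful of events, reading the cases tells more than a percentage. Protocol 8.5.4 asks for no separate SAE table, so the product-level tables add to the protocol and do not depart from it. SAEs reach the SMC in writing within 24 hours (protocol 7.4.1.4), and SMC output is set in a charter that is not among these documents.

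Most of this stands, and it limits the point to the SAE tables. It does not remove it. Severity in this trial is mild, moderate or severe, and seriousness is a separate definition (protocol 7.4.1.1), so the by-cohort TEAE tables cannot show which events were serious. The per-arm interim summary (SAP 8.1) covers C1 to C6 before C7 opens and cannot describe C7. Listings give cases without denominators.

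Three stronger readings are tempting and are not supported:

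- *That any toxicity signal at the top dose would be diluted.* Ordinary TEAEs are available by cohort.
- *That transaminase shifts are averaged over doses.* SAP 17.3 is only ambiguous, for the reasons above.
- *That Part 2 infants would enlarge the L-PZQ denominator further.* SAP 8 has the two parts analysed in turn, each standing alone, and Part 2 starts only after Part 1 has been completed and reviewed.

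**Conclusion.** The point holds for the SAE tables. A stated grouping rule pools the doses in all three, while the parallel TEAE tables are also split by cohort, so following the SAP gives no tabulated SAE rate per dose. The dilution is three-fold at most within Part 1. That figure assumes 60 dosed children in each L-PZQ arm, C7 opened, and every event in C7. It is about two-fold under the graded or background risks tried here, and at most two-fold without C7.

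For laboratory data the finding is one unclear phrase that needs settling.

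A reader might infer that the SMC would choose the dose from diluted figures. The documents do not show this: the C7 interim data are summarised per arm, and the charter that governs the other SMC output is not available. What is shown is a gap in the planned study-report tables.

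**What to change.** 1. In SAP 17.1.1 add three tables: TESAEs by cohort, by cohort and severity, and by cohort and relationship to IMP, mirroring the TEAE set. Keep the product-level TESAE tables as secondary.
2. In SAP 17.3 replace *by treatment* with *by cohort*, and apply it to both the range counts and the shift tables, so that the section matches protocol 8.5.4 ("laboratory test results and vital signs as appropriate and by treatment arm").

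The cost is a few repeated runs of existing table programs. Data collection and sample size do not change.

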### Clinical trial.gov and EudraCT -requirements

Summary tables for non-serious adverse events excluding SAEs applying frequency threshold of 5% will be provided.

## **17.1.2** Adverse Events Leading to Treatment Discontinuation

Only relevant to cohort C1, since all other cohorts will receive a single dose of IMP. All AEs leading to treatment discontinuation will be listed by SOC and PT.

## 17.2 Deaths, Other Serious Adverse Events, and Other Significant Adverse Events

## 17.2.1 Deaths

In case a subject dies during the study, "Death" will be recorded as the "Primary reason for not completing" on eCRF page "Study Termination" and a corresponding SAE will to be recorded on the eCRF with outcome "Died". Date and cause of death will be provided in individual subject data listing together with all dosing information, by cohort.

## **17.2.2 Serious Adverse Events**

Please refer to Section 17.1.1. For these TEAEs, subject listings will be provided in addition.

## 17.3 Clinical Laboratory Evaluation

Laboratory values (including corresponding normal ranges) will be used for summary statistics and shift tables.

Quantitative data will be examined for trends using descriptive statistics (mean, SD, median, Q1, Q3, minimum, and maximum) of actual values and changes from baseline to each visit over time. The changes computed will be the differences from baseline (Day 1 samples) to end-of-trial (Day 14 / early withdrawal). Qualitative data based on reference ranges will be described according to the categories (i.e. Low, Normal, High). Only the 'high' and 'low' categories will be flagged. The number of subjects with clinical laboratory values below, within, or above normal ranges at baseline compared to endpoint will be tabulated for each test by treatment. Shift tables of baseline versus endpoint (as well as the worst value at any post-baseline visit) will be presented. In case of missing data LOCF will be applied.

Laboratory values that are outside the normal range will also be flagged in the data listings, along with corresponding normal ranges. Any out-of-range values that are identified by the investigator as being clinically significant will be shown in a data listing.

Baseline (Day 1) is the last measurement prior to the first dose of any trial treatment.

Subjects without post baseline laboratory samples will be excluded from analyses with respect to change from baseline summaries.

Data will also be presented for absolute and change from baseline results using boxplots, by time point/visit.

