6.5.5 Management of Specific Adverse Events or Adverse Drug Reactions

No risk is anticipated to subjects at the tested doses of 40 and 60 mg/kg for the rac-PZQ ODTs and for the 30, 45 and 60 mg/kg dose of the L-PZQ ODTs. Subjects remain in the facility for 24

hours after dosing and will be closely observed. Safety laboratory evaluations will be conducted at the end of the confinement visit just before discharge from the hospital (i.e. at ~24 hours after dosing). In case of an AE related to liver function, the subject will be further monitored by the study team in the villages and an additional blood sample will be collected at Day 8 for liver function evaluation.

Most AEs are reported to occur directly after dosing. In addition, regular AE assessments are performed and the subjects are visited by study staff at scheduled times in the first week after dosing.

Adverse events will be managed in the participating health facility by study medical doctors who will remain in the facility during the trial.

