7.1.2 Screening

Schistosome-positive subjects after assessment by the Kato Katz method together with one of their parents/legal representatives will be invited to the study hospital. The Investigator or an appropriate designee (if local regulations permit) will obtain written informed consent to allow the participation in the study and the completion of the study procedures, from one of the parents or a legal representative of the subject as described in Section 9.2.

In the hospital, the following tests/information gathering will be performed within maximum one week prior to treatment initiation:

• Clinical safety laboratory evaluations: haematology, biochemistry and urinalysis. All biological assessments will be performed in fasting condition, if possible.

- A Rapid Diagnostic Test (RDT) to detect malaria infection (one blood sample collected by finger puncture). Treatment of concomitant diseases such as malaria will be done according to the country national guidelines. Subjects who require malaria treatment before receiving the study drug will be withdrawn from the study.
- Demographic data, consisting of date of birth, gender and height
- Medical history including occurrence of seizures consisting of all previous diseases as considered relevant (relevant defined as needing medical treatment for at least 1 week) by the Investigator
- Previous medication consisting of all previous medications within the last 6 months as considered relevant by the Investigator and all regular medications within the last 6 months.
- Complete physical examination including body weight
- Vital signs in supine position including:
 - Blood pressure (systolic and diastolic) to be assessed at least 5 minutes after resting
 - Pulse rate to be assessed at least 5 minutes after resting
 - Body temperature

Subjects who fail to meet the protocol specified criteria before first dosing or withdraw their consent in the screening period before first dosing are considered screening failures. Data to be collected from these subjects are: date of informed consent, demographics, laboratory parameters (if available), AEs and reasons for non-inclusion.

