7.1.3 Treatment period

Treatment period will last 1 day. Subjects will be hospitalized from the morning of dosing until at least 24 hours after IMP administration. During this time, subjects will be monitored for AEs.

Pre-dose assessments

Subjects will undergo physical examination, vital signs assessment and re-check of eligibility criteria. If assessments have been done on the same day they do not need to be repeated.

Post-dose assessments

Vital signs will be recorded 8 hours after first dosing. Physical examination will be performed 8 and 24 hours (\pm 10% IN HOURS) after first dosing.

Clinical safety laboratory evaluations (i.e. hematology, biochemistry and urinalysis) and urine collection for POC-CCA test will be performed 24 hours (± 10% in hours) after dosing. All biological assessments will be performed in fasting condition, if possible.

In case the participant, due to logistical or social reasons will have to spend an additional night in the hospital, the end of confinement will be documented after the specified 18/24 Hours and the

additional night will not be considered as part of confinement. As such, it will not qualify as SAE, as described in section 7.4.1.1.

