#### Handling of missing data:

Unless otherwise specified, missing data will not be replaced.

In all subject data listing, imputed values will be presented. In all listings, imputed information will be flagged.

Missing statistics, e.g. when they cannot be calculated, should be presented as "nd". For example, if n=1, the measure of variability (SD) cannot be computed and should be presented as "nd".

Where tables are presented over time, the total of missing and non-missing observations at each time-point should reflect the population still in the trial at that time. This does not apply when imputations are made beyond trial withdrawal. For example, if a subject is still in the trial at the time-point but with missing data, it should be counted in the number of missing observations.

Trial day / Treatment day are defined relative to the date of start of treatment. Trial day 1 defines the day of randomisation, the day before is defined as Trial day -1 (no Trial day 0 is defined). Treatment day will be calculated accordingly, i.e. treatment day 1 is defined as the date of first administration of IMP to any one of the study cohorts, C1-C9. Treatment duration will be one day only.

If required for an analysis, incomplete date or date/time fields will be imputed as follows:

- Missing start dates will default to the first day of the month and first month of the year, if month is missing, subject to the following exceptions:
  - If and AE/concomitant medication/procedure start date is missing and month is the same as the month of IMP administration, then the start date will default to the IMP start date. If the month is different, the start date will default to the first day of the month.
  - If start date and month is missing and stop date is not before first IMP administration, then the start date will default to the IMP start date.
  - If start date and month and stop date is missing, then the start date will default to the IMP start date.
  - Missing start dates for medical history and medications stopped prior to IMP administration will not be imputed.
- Missing stop dates will default to the last day of the month and last month of the year, if month is missing, subject to the following exceptions:
  - If stop date is missing for a known medical history/previous medication, then the stop date will default to the IMP start date 1 day.

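### SAP 17.3 sets the laboratory change and shift endpoint at Day 14 with LOCF, but the only safety laboratory sample scheduled after Day 2 is a conditional one at Day 8

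*SAP*

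**What the plan says.** SAP 17.3 plans several laboratory outputs. By-visit summaries cover "actual values and changes from baseline to each visit over time". The end-of-trial change is defined next: "The changes computed will be the differences from baseline (Day 1 samples) to end-of-trial (Day 14 / early withdrawal". Shift tables then compare baseline with endpoint and baseline with the worst post-baseline value. Endpoint is not defined separately, so it is most naturally read as the end-of-trial point just named. On gaps, the section says "In case of missing data LOCF will be applied". This overrides the general rule in SAP section 11: "Unless otherwise specified, missing data will not be replaced". Children with no post-baseline laboratory sample are left out of the change summaries.

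The protocol places the tests as follows. Section 7.1.2 lists "Clinical safety laboratory evaluations: haematology, biochemistry and urinalysis" among the procedures that "will be performed within maximum one week prior to treatment initiation". Section 7.1.3 states: "Clinical safety laboratory evaluations (i.e. hematology, biochemistry and urinalysis) and urine collection for POC-CCA test will be performed 24 hours" after dosing, with a 10% tolerance. Section 6.5.5 agrees: "Safety laboratory evaluations will be conducted at the end of the confinement visit just before discharge". Section 5.2.1 likewise puts the repeat test at the end of the hospital stay. A further blood sample at Day 8 is conditional on an AE.

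**The concern.** The SAP names an endpoint at which the schedule collects no laboratory data. Changes in laboratory parameters are a named safety endpoint (SAP section 17), and the results are intended for the clinical study report. If the gap is filled by LOCF, a summary headed end-of-trial would consist of results from about one day after dosing, plus Day 8 results for children who were sampled because something had gone wrong. A reader could take it as evidence on laboratory safety two weeks after treatment, which the scheduled sampling cannot provide. The time after dosing would also differ between children within one column, and the difference would depend on their AE history.

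**Working it through.** The plan gives no figure to reproduce, so the check sets the sources side by side for safety laboratory tests (haematology, biochemistry, urinalysis).

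| Protocol source | Pre-dose | Day 2 | Day 8 | D14-D21 |
|---|---|---|---|---|
| Appendix II, C1 | D1 | yes (16 h after third dose) | conditional | none |
| Appendix II, C2-C7 | D1 | yes (24 h) | conditional | none |
| Appendix II, C8-C9 | D-7 to D1 | yes (24 h) | conditional | none |
| Appendix III, C1-C7 | yes | yes | POC-CCA urine only | Kato-Katz stool and POC-CCA urine only |
| Appendix III, C8-C9 | yes | yes | POC-CCA urine only | Kato-Katz stool and POC-CCA urine only |
| Sections 7.1.2 to 7.1.4 | within one week | 24 h ± 10% | biochemistry, after a liver-function AE before discharge | stool, POC-CCA urine, vital signs, physical examination |

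**Count.** A D14-D21 safety laboratory test appears in 0 of 3 Appendix II tables and 0 of 2 Appendix III lists. The early-withdrawal alternative adds none, because 7.1.4 gives that visit the End of Study procedures. Planned children: 360 + 40 = 400 without C7, and 420 + 40 = 460 with C7.

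**What LOCF would carry.** The change summaries exclude children without a post-baseline sample, so the value carried into them is a post-dose one. It is the Day 2 value, unless a conditional Day 8 value exists.

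**Age of the carried value against the Day 14 label.**
- Day 2: 14 − 2 = 12 days.
- Day 8: 14 − 8 = 6 days. With the ± 1 day that 7.1.4 allows, this is 14 − 9 = 5 to 14 − 7 = 7 days.

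**Time of the Day 2 sample.** In the single-dose cohorts it is 24 × 0.9 = 21.6 h to 24 × 1.1 = 26.4 h after dosing. C1 has doses at H0, H4 and H8 in Appendix II, and its sample is 16 h after the third. That is 8 + 16 = 24 h nominally after the first dose, so the 21.6 to 26.4 h range should not be read as time since last dose in C1.

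**Which tests have mixed timing.** As 7.1.4 is worded, the Day 8 sample is for biochemistry, which means the seven tests in Annexe IV. The Appendix II footnotes attach to the whole laboratory row, so on that reading haematology and urinalysis could be affected too. The share of children with a Day 8 value cannot be derived from the documents.

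**Text pointing the other way.** Section 7.4.3 speaks of safety laboratory parameters analysed at screening and at the End of Study visit. That sentence describes the content of a laboratory manual, and the same section refers sampling to Appendix II. Section 7.1.4 includes safety laboratory tests among ongoing abnormal findings at the End of Study visit that are to be followed up. This can refer to earlier abnormalities that have not resolved. Neither passage schedules a sample.

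**A smaller mismatch.** SAP 17.3 says Day 14, while the SAP section 11 window for the End of Study visit is Day 14 to 21, plus 3 days.

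**The case against.** The best counter-argument is that the protocol is itself unclear. Both 7.4.3 and 7.1.4 connect laboratory tests with the End of Study visit, the laboratory manual is not available, and SAP 17.3 may simply follow an intention that the schedule tables failed to record. This stands in part. It means that reconciliation must come before any change of endpoint. It does not rescue the current text, because if a sample was intended, the schedule tables are incomplete.

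It can also be said that the outputs are descriptive, that Day 2 results appear under their own visit, that the worst-value shift table keeps any Day 2 abnormality, and that no table titles are given in the documents. All of this is correct and limits the harm. The label still comes from SAP 17.3 itself, which calls the result an end-of-trial change.

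Protocol 8.5.1 also prescribes LOCF for continuous endpoints. That rule covers a missing post-baseline measurement. It is no reason to create a visit at which no child is due to be sampled.

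A reader might go further and infer that the end-of-trial tables would be empty, on the view that an unscheduled test is not missing data. The SAP does not rule this out expressly, but it is the less natural reading, given the explicit LOCF rule and the exclusion only of children without any post-baseline sample. Nor do the documents support the inference that laboratory safety data would be lost.

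**Conclusion.** The mismatch is certain on the schedule: no D14-D21 safety laboratory sample for any cohort, against a laboratory endpoint that SAP 17.3 places at that visit. On the natural reading, two descriptive outputs, the end-of-trial change summary and the endpoint shift table, would present Day 2 values with some AE-triggered Day 8 values as end-of-trial results. No observation is lost and no efficacy result is touched.

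This rests on reading endpoint as end-of-trial, and on applying LOCF to a visit that has no scheduled sample. A reader might infer that these tables would steer the Safety Monitoring Committee's dose recommendation for Part 2. The committee's charter is not among the documents, so that is not established. Nor do the documents show whether an End of Study sample was intended. The point should be corrected because the text is wrong as it stands and the correction is nearly free.

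**What to change.** 1. Reconcile protocol 7.4.3 and the follow-up sentence in 7.1.4 with Appendices II and III, and state whether an End of Study safety laboratory sample exists.
2. Unless one is confirmed, define the change and shift endpoint in SAP 17.3 as the last pre-dose sample to the observed Day 2 sample. Drop LOCF for laboratory data, keep the worst post-baseline shift, and report Day 8 values separately as conditional follow-up. Title each table by actual sampling day.
3. If an End of Study sample is confirmed, correct the schedule tables and report it as its own observed visit, with the day window used in SAP section 11.
4. As a minor item, reconcile the wording of the Day 8 test. Sections 6.5.5 and 7.1.4 tie it to a liver-function AE, while the Appendix II footnotes refer to AE follow-up in general.

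The cost is a few sentences in SAP 17.3, table titles, and short protocol clarifications. Observed data do not change. No new samples are needed unless the sponsor confirms that an End of Study sample was intended.
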